If all three dose levels are administered, the minimum number of patients enrolled will be 9 per arm and the maximum number of patients will be 18 per arm.

Estimated Duration of the Study

Based on projections from current clinical practice, it is anticipated that the accrual will take 12-18 months to complete.

Summary of Subject Eligibility Criteria:

Inclusion Criteria

- Patients must have presumed malignant glioma based on clinical and radiologic evaluation (pathologic confirmation of malignant glioma must be made at the time of stereotactic biopsy or resection prior to NSC-CRAd-S-pk7 injection; if this is not possible, the injection will not be performed and the subject will no longer be eligible for the study).
- Tumor must be accessible for injection and must not be located in the brainstem, or contained within the ventricular system.
- Planning to undergo standard radiation/chemotherapy
- 18 years of age or older.
- Performance status must be KPS \geq 70
- SGOT (AST) $<$ 3x upper limit of normal
- Serum creatinine $<$ 2mg/dl
- Platelets $>$ 100,000/mm³ and WBC $>$ 3000/mm³

Exclusion Criteria

- Prior or ongoing liver disease including known cirrhosis, hepatitis B or C infection but not to exclude patients with a distant history of resolved hepatitis A infection.
- Immunosuppressive drugs (with exception of corticosteroid).
- Known HIV+ patients.
- Acute infections (viral, bacterial or fungal infections requiring therapy).
- Pregnant or breast-feeding patients.
- Evidence of metastatic disease or other malignancy (except squamous or basal cell skin cancers).
- Prior radiation therapy to the brain or prior treatment for brain tumor
- Other serious co-morbid illness or compromised organ function.

Investigational Product Dosage and Administration:

Table 1 – Dose Escalation Schema

Cohort	Number NSCs Injected	Total Viral Dose Viral particles (vp)/patient
1	50 million (5×10^7)	6.25×10^{10}
2	100 million (1×10^8)	1.25×10^{11}
3	150 million (1.5×10^8)	1.875×10^{11}

Clinical Observations and Tests to be Performed:

- On day 0, stereotactic biopsy or resection of the tumor
- History and physical will be performed weekly, 2-4 weeks after completion of radiation and at least every 3 months for the first year.
- Quality of life questionnaire (FACT-Br version 4) once during week 2-3, 2-4 weeks after completion of radiation and every 3 months for the first year or until disease progression.

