1.0 INTRODUCTION – BACKGROUND & RATIONALE

1.1 Disease Background

Brain tumors are a relatively common malignancy for which standard treatments do not provide satisfactory median or long-term results. There are an estimated 17,000 new cases and 13,100 deaths from primary nervous system tumors in 2007, the majority of which are malignant gliomas (American Cancer Society). Slower growing, less aggressive gliomas are referred to as low grade or benign, whereas higher grade, malignant gliomas include malignant astrocytomas (36% of gliomas) and glioblastoma multiforme (GBM; 47% of gliomas and 21.7% of all primary brain tumors) (Levin et al, 2001). Therapy, including surgery, radiation and chemotherapy, is essentially palliative. Although neoplasms located within the frontal, temporal or occipital poles of the brain are amenable to “gross total resection” (GTR), these operations provide little control to the microscopic foci of tumor outside the main mass. Many malignant gliomas located within the corpus callosum, basal ganglia, brainstem and areas of eloquent cortex (speech, motor or visual

areas) are not resectable. For both GTR and non-resectable masses, radiation therapy is the major therapy provided after diagnosis. Its efficacy is limited by the low radiation sensitivity of tumor cells and the inclusion of normal brain tissue within radiation fields (Levin et al, 2001). With conventional radiation therapy, the median survival time for patients with anaplastic astrocytoma is 36 months, and the 3-year survival rate is approximately 55%. (Prados et al, 1999). In contrast, the median survival time for patients with GBM is 10 months and the 3-year survival rate is only 6% (Leibel et al, 1994).

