3.0 PATIENT ELIGIBILITY

The target population for this study is patients with newly diagnosed malignant glioma. This will be a single-center trial conducted at Northwestern Memorial Hospital and Northwestern Medicine Neurological Surgery clinic of Northwestern University.

Up to 36 subjects will be included in this trial. Approximately 6 potentially eligible patients are seen per month, and it is anticipated that at least 1 per month will be accrued. Potential patients are under the direct care of the Principal Investigator (PI) at Northwestern University, [name] at [contact].

Eligibility will be evaluated by the study team according to the following criteria. Eligibility waivers are not permitted. Subjects must meet all of the inclusion and none of the exclusion criteria to be registered to the study. Study treatment may not begin until a subject is registered. Please refer to Section 11 for complete instructions regarding registration procedures.

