3.1 Inclusion Criteria

3.1.1 Patients must have a presumed newly identified malignant glioma based on clinical and radiologic evaluation. Pathologic confirmation of malignant glioma must be made at the time of stereotactic biopsy or resection on frozen section by a neuropathologist prior to NSC-CRAd-S-pk7 injection; if this is not possible, the injection will not be performed and the subject will no longer be eligible for the study.

3.1.2 Patients must be planning to undergo standard radiation/chemotherapy.

3.1.3 The tumor must be accessible for injection.

3.1.4 Patients must be age \geq 18 years.

3.1.5 Patients must exhibit a Karnofsky performance status of \geq 70.

3.1.6 Patients must have adequate organ and bone marrow function within 28 days prior to registration, as defined below:

- SGOT (AST) $<$ 3x upper limit of normal

- Serum creatinine $<$ 2mg/dl

- Platelets $>$ 100,000/mm³ and WBC $>$ 3000/mm³

3.1.7 Be able to undergo a brain magnetic resonance imaging scan.

3.1.8 Females of child-bearing potential (FOCBP) and males must agree to use adequate contraception (hormonal or barrier method of birth control; abstinence) prior to study entry, for the duration of study participation, and for 90 days following completion of therapy. Should a female patient become pregnant or suspect she is pregnant while participating in this study, she should inform her treating physician immediately.

NOTE: A FOCBP is *any woman* (regardless of sexual orientation, having undergone a tubal ligation, or remaining celibate by choice) who meets the following criteria:

- Has not* undergone a hysterectomy or bilateral oophorectomy
- Has had* menses at any time in the preceding 12 consecutive months (and therefore has not been naturally postmenopausal for $>$ 12 months)

3.1.9 FOCBP must have a negative pregnancy test within 7-10 days prior to receiving study drug.

3.1.10 Patients must have the ability to understand and the willingness to sign a written informed consent prior to registration on study.

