3.2 Exclusion Criteria

- 3.2.1 Tumor which invades the ventricular system.
- 3.2.2 Have had prior radiation therapy to the brain or prior treatment for their brain tumor (except prior biopsy or subtotal resection).
- 3.2.3 Planning to undergo additional treatment for the brain tumor other than standard of care
- 3.2.4 Prior or ongoing liver disease including known cirrhosis, active hepatitis B or C infection; not to exclude patients with a distant history of resolved hepatitis A infection.
- 3.2.5 Known known human immunodeficiency virus (HIV) infection.
- 3.2.6 Evidence of metastatic disease or other malignancy (except squamous or basal cell skin cancers).
- 3.2.7 Patients receiving any other investigational agents.
- 3.2.8 Currently taking immunosuppressive drugs within 28 days of study product injection (with exception of corticosteroids).
- 3.2.9 Patients who have a history of allergic reactions attributed to compounds of similar chemical or biologic composition to temozolomide are not eligible.
- 3.2.10 Patients who have an uncontrolled intercurrent illness including, but not limited to any of the following, are not eligible:
 - Acute hypertension requiring control with intravenous medication
 - Ongoing or active infection requiring systemic treatment
 - Symptomatic congestive heart failure
 - Unstable angina pectoris
 - Unstable cardiac arrhythmia
 - Psychiatric illness/social situations that would limit compliance with study requirements
 - Any other illness or condition that the treating investigator feels would interfere with study compliance or would compromise the patient's safety or study endpoints
- 3.2.11 Female patients who are pregnant or nursing are not eligible.

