4.1 Overview

This study is an open label, Phase I, dose-escalation gene therapy clinical trial with two arms:

1. **Arm A** – Unresectable disease, will receive stereotactic intratumoral injection of NSC-CRAd-S-pk7 immediately following stereotactic biopsy confirmation of clinical diagnosis
2. **Arm B** – Resectable or partially resectable disease, will receive injection of NSC-CRAd-S-pk7 into remaining tumor or tumor bed after resection.

Pathologic confirmation of a malignant glioma must be made at the time of surgery prior to injection. If this is not possible, the injection will not be performed and the patient will no longer be eligible for the study. In the event that the final pathology reading reveals anything other than a malignant glioma, the patient will be removed from the protocol but will continue to be followed for toxicity. Patients having not received any study treatment will need to be replaced and will not be counted as one of the minimum number required without DLT for advancement to the next dose level but will be counted if a DLT is experienced.

Standard radiotherapy and chemotherapy will begin 10-14 days after NSC-CRAd-S-pk7 injection. Long-term follow-up of general health status and any side effects may continue for life. This will be done by telephone contact or letter with the patient or their primary care physician. Medical records will also be reviewed to assess for any potential side effects and for general health status.

An attempt will be made to perform a complete autopsy on any patient who dies, if consent is given by the legally authorized representative. In addition to standard pathological examinations, tissues will be taken for additional studies such as analysis of CRAd-S-pk7 presence and expression.

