4.3 Toxicity Management and Dose Delays or Modifications

Any patient who receives an injection of NSC-CRAd-S-pk7 will be evaluable for toxicity endpoints. In the event that the final pathology reading reveals anything other than a malignant glioma, the patient will be removed from the protocol but will continue to be followed for toxicity. Such a patient will not be counted as one of the minimum number required without DLT for advancement to the next dose level but will be counted if a DLT is experienced. Each patient will be assessed for the development of toxicity according to the timeframe referenced in the Schedule of Events table. Treatment all toxicity events, based on CTCAE v4.03 criteria, will be managed according to institutional guidelines.

There will be no dose delays or modifications as this is a single-dose therapy.

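### Section 3, the list used to register patients, omits the Study Summary's requirement that the tumor not be in the brainstem

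*Combined protocol and SAP*

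**What the plan says.** The eligibility list in the Study Summary puts three location conditions in one inclusion criterion: "Tumor must be accessible for injection and must not be located in the brainstem, or contained within the ventricular system".

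Section 3.0 makes the numbered lists in 3.1 and 3.2 the basis for registration: "Eligibility will be evaluated by the study team according to the following criteria. Eligibility waivers are not permitted". The item matching the first condition is "3.1.3 The tumor must be accessible for injection". The item matching the ventricular condition is 3.2.1: "Tumor which invades the ventricular system". No item matches the brainstem condition.

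The only other mention of the brainstem in the available text is in Section 1.1, which names it among sites where surgery is often not possible: "Many malignant gliomas located within the corpus callosum, basal ganglia, brainstem and areas of eloquent cortex". Under Section 4.1, unresectable disease defines Arm A, which is treated by stereotactic intratumoral injection.

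**The concern.** A summary may leave out detail that the full list contains. It should not hold a restriction that the full list lacks, because staff who confirm eligibility work from the full list. Here someone applying Section 3 literally could register a patient whom the Study Summary rules out.

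The case is foreseeable, since the protocol's own background places brainstem gliomas among tumors that are often unresectable, which is the Arm A population. The product is given once: "There will be no dose delays or modifications as this is a single-dose therapy". A registration made under the less restrictive text cannot be put right after injection. That is true of any eligibility error in a single-dose trial, but it is a reason to have the rule in the list that is actually used.

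**Working it through.** No arithmetic beyond counting applies, and the plan states no figure to reproduce. The check sets the two lists side by side.

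**Step 1: count the registration criteria.** Section 3.1 runs from 3.1.1 to 3.1.10, which is 10 items. Section 3.2 runs from 3.2.1 to 3.2.11, which is 11 items. 10 + 11 = 21. Items naming the brainstem: 0 of 21.

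**Step 2: split the Study Summary's location criterion and look for each part in Section 3.**

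| Condition in the Study Summary | Counterpart in Section 3 |
|---|---|
| Accessible for injection | 3.1.3 |
| Not contained within the ventricular system | 3.2.1 (worded as invasion) |
| Not located in the brainstem | None |

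**Step 3: check whether the Study Summary is simply a loose paraphrase throughout.** Its other criteria all have a counterpart, some reworded: diagnosis 3.1.1, planned radiation and chemotherapy 3.1.2, age 3.1.4, KPS 3.1.5, laboratory limits 3.1.6, prior treatment 3.2.2, liver disease 3.2.4, HIV 3.2.5, other malignancy 3.2.6, immunosuppressants 3.2.8, infection and comorbidity 3.2.10, pregnancy 3.2.11. The brainstem condition is the only one with none.

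**Step 4: follow a test case.** Take a patient with a presumed malignant glioma of the brainstem, not resectable, reachable by stereotactic needle, not invading the ventricles, and otherwise eligible.

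- Study Summary: not eligible.
- 3.1.3: met, because the tumor is reachable.
- 3.2.1: not triggered.
- The remaining criteria: none refers to brainstem location.
- Section 4.1: "Pathologic confirmation of a malignant glioma must be made at the time of surgery prior to injection". This tests histology, not site.

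The patient meets the explicit Section 3 criteria and would be assigned to Arm A.

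**Step 5: list what could still stop registration or injection.**

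- A judgment under 3.1.3 that the tumor is not accessible.
- The last bullet of 3.2.10, which begins "Any other illness or condition that the treating investigator feels would interfere with study compliance" and goes on to patient safety. It depends on the treating investigator's view and sits under uncontrolled intercurrent illness.
- The surgeon's choice of target under Section 4.4.
- The signed eligibility checklist and the QAM's source review under Section 11.3.1. The checklist content is not in the documents, so it may or may not carry the item.

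The first three are discretionary. The fourth cannot be assessed from the documents.

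**The case against.** The strongest reply is that nothing is in conflict. Only the Study Summary speaks about the brainstem, and it forbids such tumors; Section 3 is silent and nowhere admits them. Excluding brainstem tumors complies with both, and Section 11.6, which requires conduct as the approved protocol describes, takes in the Study Summary too. This stands. A reader might infer that the protocol contradicts itself, but the documents show an omission.

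Three other strong readings also go too far.

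- *A safety exclusion was lost.* The Study Summary lists the condition under inclusion and gives no reason for it. Safety is a sensible guess at the motive, but it is not stated.
- *The surgeon's avoidance list in Section 4.4 confirms the gap, because it names the ventricle and not the brainstem.* That list says where the needle should not deliver product. The eligibility rule says where the tumor may not be. Comparing like with like, the ventricular condition has one counterpart (3.2.1) and the brainstem condition has none.
- *Ineligible patients will be injected, or the MTD will be distorted.* The trial is single-center, in patients under the investigator's direct care, with a screening MRI and several points of judgment before injection. The documents give no frequency for accessible brainstem gliomas, and nothing suggests that one would be enrolled.

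It can also be said that Section 3 may be the newer list and the Study Summary out of date. Other wording differences would fit that: 3.2.2 allows prior biopsy or subtotal resection, and 3.2.4 limits hepatitis B or C to active infection. The documents do not settle the point. If so, the Study Summary is the text that needs correcting.

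The argument that accessibility already covers the brainstem does not stand. The Study Summary states accessibility and brainstem location as separate conditions, so one was not meant to imply the other.

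**Conclusion.** Wrong as written: an eligibility rule is stated in one place and missing from the list that governs registration. The size is one of the three location conditions in the Study Summary, with 0 of 21 Section 3 criteria carrying it. The practical exposure is confined to an unresectable brainstem tumor judged reachable for Arm A injection, where exclusion rests on discretion or on a checklist that cannot be seen. No endpoint, dose rule, sample size or analysis figure changes, and no number of affected patients is claimed.

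The conclusion assumes that the supplied text of the Study Summary and Section 3 is complete, and that registration follows Section 3 as Section 3.0 says. It would lose most of its practical weight if the eligibility checklist already names the brainstem, though the protocol text would still need aligning.

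**What to change.** Ask the sponsor whether the brainstem condition was dropped on purpose.

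- If not, add a numbered item to Section 3.2: *Tumor located in the brainstem.*
- If so, delete the condition from the Study Summary and give the reason.

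Until this is answered, apply the stricter Study Summary rule, and check that the eligibility checklist carries the item. As minor housekeeping, use one wording for the ventricular condition in the Study Summary and 3.2.1, since being contained within the ventricles and invading them are not the same test.

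The cost is one wording amendment and a check of the checklist. No new procedure is needed, because location can be read from the screening MRI already required in Section 5.0, Table 3. Adding the item should have little or no effect on accrual, because the Study Summary already excludes these patients.

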3.2 Exclusion Criteria

- 3.2.1 Tumor which invades the ventricular system.
- 3.2.2 Have had prior radiation therapy to the brain or prior treatment for their brain tumor (except prior biopsy or subtotal resection).
- 3.2.3 Planning to undergo additional treatment for the brain tumor other than standard of care
- 3.2.4 Prior or ongoing liver disease including known cirrhosis, active hepatitis B or C infection; not to exclude patients with a distant history of resolved hepatitis A infection.
- 3.2.5 Known known human immunodeficiency virus (HIV) infection.
- 3.2.6 Evidence of metastatic disease or other malignancy (except squamous or basal cell skin cancers).
- 3.2.7 Patients receiving any other investigational agents.
- 3.2.8 Currently taking immunosuppressive drugs within 28 days of study product injection (with exception of corticosteroids).
- 3.2.9 Patients who have a history of allergic reactions attributed to compounds of similar chemical or biologic composition to temozolomide are not eligible.
- 3.2.10 Patients who have an uncontrolled intercurrent illness including, but not limited to any of the following, are not eligible:
 - Acute hypertension requiring control with intravenous medication
 - Ongoing or active infection requiring systemic treatment
 - Symptomatic congestive heart failure
 - Unstable angina pectoris
 - Unstable cardiac arrhythmia
 - Psychiatric illness/social situations that would limit compliance with study requirements
 - Any other illness or condition that the treating investigator feels would interfere with study compliance or would compromise the patient's safety or study endpoints
- 3.2.11 Female patients who are pregnant or nursing are not eligible.

4.0 TREATMENT PLAN

Diagnostic or laboratory studies performed exclusively to determine eligibility for this trial will be done only after obtaining written informed consent. Studies or procedures that were for clinical indications (not exclusively to determine study eligibility) may be used for baseline values, even if the studies were done before informed consent was obtained. Reference is made to Section 10.0 – Study Calendar.

4.1 Overview

This study is an open label, Phase I, dose-escalation gene therapy clinical trial with two arms:

1. **Arm A** – Unresectable disease, will receive stereotactic intratumoral injection of NSC-CRAd-S-pk7 immediately following stereotactic biopsy confirmation of clinical diagnosis
2. **Arm B** – Resectable or partially resectable disease, will receive injection of NSC-CRAd-S-pk7 into remaining tumor or tumor bed after resection.

Pathologic confirmation of a malignant glioma must be made at the time of surgery prior to injection. If this is not possible, the injection will not be performed and the patient will no longer be eligible for the study. In the event that the final pathology reading reveals anything other than a malignant glioma, the patient will be removed from the protocol but will continue to be followed for toxicity. Patients having not received any study treatment will need to be replaced and will not be counted as one of the minimum number required without DLT for advancement to the next dose level but will be counted if a DLT is experienced.

Standard radiotherapy and chemotherapy will begin 10-14 days after NSC-CRAd-S-pk7 injection. Long-term follow-up of general health status and any side effects may continue for life. This will be done by telephone contact or letter with the patient or their primary care physician. Medical records will also be reviewed to assess for any potential side effects and for general health status.

An attempt will be made to perform a complete autopsy on any patient who dies, if consent is given by the legally authorized representative. In addition to standard pathological examinations, tissues will be taken for additional studies such as analysis of CRAd-S-pk7 presence and expression.

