4.2.1 Definitions of Dose-limiting Toxicities

- Subjects will be evaluated for dose-limiting toxicities (DLT period) from the time of signing informed consent through completion of concomitant radiation and temozolomide.
 - DLTs will be evaluated using CTCAE v 4.03 criteria
 - The DLT will be defined as any of the following:
 - Toxicity attributed to study product
 - Any grade 3 toxicity including hematologic and non-hematologic toxicities
 - Any grade 3 toxicity related to the intervention requiring interruption or delay in radiation therapy for more than seven days except CNS hemorrhage*
- * Grade 3 (asymptomatic) radiologic evidence of CNS hemorrhage (commonly seen after biopsy) is not a DLT. Grade 4 (symptomatic) CNS hemorrhage is a DLT. Assessment of neurological toxicity relates to the relative changes from the pre-treatment neurological status. Other anticipated toxic phenomena that are not related directly to viral transduction of the brain tumor or neurological complications which can be explained by the presence of the mass lesion and are compatible with the natural history of malignant brain tumors may require cessation of treatment in individual patients. Such occurrences would not be considered DLT unless they occur with a greater frequency than expected in this patient population.
- A safety analysis will take place 14 days after the first and second subjects receive treatment, and before moving to the next higher viral dose level. The DMC will assess the safety of administering NSC-CRAd-S-pk7 in future patients either at the same dose or a modified dose. No patients will receive treatment until the DMC provides their recommendation.
 - The maximally tolerated dose is defined as the dose level immediately below the dose where the DLT was observed.

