7.1 Adverse Event Monitoring

Adverse event data collection and reporting, which are required as part of every clinical trial, are done to ensure the safety of subjects enrolled in the studies as well as those who will enroll in future studies using similar agents. Adverse events are reported in a routine manner at scheduled times during a trial (from screening through the Day 56 visit). In addition, certain adverse events must be reported in an expedited manner to allow for optimal monitoring and patient safety and care.

All patients experiencing an adverse event, regardless of its relationship to study drug, will be followed until:

- the adverse event resolves or the symptoms or signs that constitute the adverse event return to baseline;
- any abnormal laboratory values have returned to baseline;
- there is a satisfactory explanation other than the study drug for the changes observed; or
- death.

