8.1.5 Protocol dose specifics

Temozolomide is dosed at 75 mg/m² daily for up to 49 days, concomitant with focal radiotherapy. After a break of 4 weeks, temozolomide maintenance therapy is given for up to 6 cycles. Initial dose is 150 mg/m² with an increase to 200 mg/m² if tolerated, given as a single daily dose for 5 days every 28 days. Timing of daily administration will be per routine use and as directed by the treating

oncologist. Temozolomide dose may be delayed or modified by the treating oncologist based on patient tolerance.

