10.3.1 Analysis Datasets

All the analysis will be conducted in the safety population, including all the patients who received at least one dose of NSC-CRAd-S-pk7.

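### The protocol's sections disagree on who enters the 3+3 DLT count and from when, and they set no follow-up or replacement rule for an injected patient who leaves early without a DLT

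*Combined protocol and SAP*

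**What the plan says.** Five places in the protocol bear on the DLT count.

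- **Section 4.1**, on patients who were never treated: "Patients having not received any study treatment will need to be replaced and will not be counted as one of the minimum number required". The same sentence nevertheless brings such a patient into the count if a DLT occurs.
- **Section 4.2.1**, on the DLT period: it runs "from the time of signing informed consent through completion of concomitant radiation and temozolomide". Table 3 puts consent in the screening window, Day -28 to Day -1.
- **Section 4.3**, on evaluability: "Any patient who receives an injection of NSC-CRAd-S-pk7 will be evaluable for toxicity endpoints". It then gives the not-counted-unless-DLT rule for patients whose final pathology is not malignant glioma. Section 10.2 repeats the rule for that same group.
- **Section 4.2**, note after Table 2: the level declared the MTD needs six patients treated at it. Completed follow-up is not mentioned.
- **Section 10.3.1**: all analyses use the safety population, "including all the patients who received at least one dose of NSC-CRAd-S-pk7".

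On timing, Section 7.1 sets routine AE reporting "from screening through the Day 56 visit". Section 4.6.2 starts radiation 10-14 days after injection. The temozolomide part of Section 8 (numbered 8.1.5, under 8.2) allows dosing "daily for up to 49 days, concomitant with focal radiotherapy".

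**The concern.** The MTD is the primary endpoint, and it follows mechanically from counts in groups of three to six patients. One patient wrongly in or out of the count can change a dose decision, so the rule for who is counted, and over what period, has to be single and complete.

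The gaps pull in opposite directions. If untreated patients and pre-injection time can contribute DLTs, surgical or disease events may be charged to the product and escalation may stop too soon. If an injected patient who leaves early can stand as DLT-free, or a late event falls outside routine AE reporting, DLTs may be missed and escalation comes too readily. The two errors cannot be assumed to cancel.

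**Working it through.** **1. The plan's own figures.** With true DLT rate p, the 3+3 rule gives

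P(escalate) = (1-p)^3 + 3p(1-p)^2 × (1-p)^3.

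For p = 20, 30, 40, 50 and 60% this is 70.9, 49.4, 30.9, 17.2 and 8.2%. Table 10 prints 71, 49, 31, 17 and 8%, so it is reproduced. The formula assumes that every counted patient is fully observed for product DLTs.

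**2. Who is counted.**

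| Section | Group | Counted if no DLT | Counted if DLT |
|---|---|---|---|
| 4.1 | Received no study treatment | No, replaced | Yes |
| 4.3, 10.2 | Final pathology not malignant glioma | No | Yes |
| 4.3 | Any injected patient | Evaluable; no minimum follow-up | Evaluable |
| 10.3.1 | Injected patients | In the analysis | In the analysis |

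The 4.1 row cannot be squared with the 10.3.1 row: an untreated patient's DLT would enter the dose decision but no analysis. Such patients will exist, because injection requires frozen-section confirmation (Sections 3.1.1 and 4.1), so some may have a biopsy or resection and no injection.

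**3. Can an untreated patient have a DLT?** Section 4.2.1 lists toxicity attributed to the product, any grade 3 toxicity, and related grade 3 toxicity that delays radiation. The list as published does not show whether the second item stands alone or sits under the first.

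- If it stands alone, a grade 3 event between consent and injection qualifies. The note to the list also calls symptomatic grade 4 CNS hemorrhage a DLT without restating attribution.
- If attribution governs every item, an untreated patient can never have a DLT and the 4.1 clause has no content.

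Either way the text needs correcting.

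**4. Injected patients who leave early.** Section 4.1 replaces only untreated patients. Section 4.3 withholds only the non-glioma group from the DLT-free minimum. Section 10.3.2.2 mentions non-completion of RT/TMZ, but only as a trial-level stop and review above two patients. No section says how one injected early leaver without a DLT is counted.

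**5. End of the DLT period against Day 56.** Start s is Day 10 or 14, with five fractions a week; each range covers weekday starts.

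- 200 cGy to 5500-6000 cGy (Section 4.6.2): 28-30 fractions. The last day is s+37 to s+39 for 28 and s+39 to s+41 for 30, giving Day 47-55.
- TMZ for 42 days: s+41 = Day 51-55. For 49 days: s+48 = Day 58-62.
- 1.8 Gy, the lower end of the range in Table 3, to 6000 cGy: 34 fractions, s+45 to s+47 = Day 55-61.
- An 8-day delay, the shortest exceeding seven days, at 200 cGy: 47+8 to 55+8 = Day 55-63.

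The nominal course fits within Day 56. With 49 days of TMZ it overruns by 2-6 days. The last two cases may overrun.

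**6. Size, under assumed rates.** The documents give no rate of non-product events or early leaving.

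- Non-product events at rate b: effective rate 1-(1-p)(1-b). At p = 10% and b = 0, 5 and 10%, the rate is 10, 14.5 and 19%, and P(escalate) is 91, 82 and 73%.
- Leavers at rate q, counted DLT-free with none of their DLTs seen: effective rate p(1-q). At p = 50% and q = 0, 10 and 30%, the rate is 50, 45 and 35%, and P(escalate) is 17, 23 and 40%. If half their DLTs are seen, the rate is p(1-q/2) and the last two become 20 and 27%.
- One untreated patient's DLT counted within the first group, with that patient replaced: escalation then needs no DLT in six injected patients. At p = 20% that is 0.8^6 = 26%, against 71%.

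**The case against.** The 4.1 sentence looks like a drafting slip, since Sections 4.3 and 10.2 attach the same rule to the non-glioma group. Attribution is named in the first and third DLT items, and the note excludes asymptomatic bleeding after biopsy and events explained by the tumor mass. That stands, and it narrows the point: the contradiction is one to reconcile and does not show a deliberate choice.

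A reader might infer that early leavers count as DLT-free. No section says so. Section 4.3 itself separates being evaluable for toxicity from counting towards the DLT-free minimum. There are also safeguards:

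- a death within 56 days halts enrollment pending DSMB review (Section 7.0);
- the DMC reviews safety before each higher level (Section 4.2.1);
- patients who stop treatment may still give follow-up data (Section 4.10);
- more than two RT/TMZ non-completers stop the trial for review (Section 10.3.2.2). At 30% leaving, 18 patients in an arm would give 18 × 0.30 = 5.4 expected non-completers, so a rate that high would not pass unnoticed.

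None of these says whether the individual patient fills a place in the cohort.

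A reader might also infer that AE collection always stops before the DLT period ends. It does not for the nominal course. Section 4.2.1 itself requires DLT evaluation to the end of RT/TMZ, Section 11.4 requires weekly data submission meanwhile, Table 5 marks AEs at Day 56 and every eight weeks after, and Section 7.3.2 keeps attributed later events reportable. A delay DLT is also met once the delay passes seven days, not when the course ends. The Day 56 point is therefore conditional. It remains because Section 7.1 names a fixed day while the DLT period has a variable end.

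**Conclusion.** The concern holds as a conflict and a gap in the counting rules. Sections 4.1, 4.3, 10.2 and 10.3.1 disagree on whether an untreated patient can enter the DLT count. Section 4.2.1 starts the period at consent. An injected patient who leaves before the end of RT/TMZ without a DLT has no follow-up or replacement rule and can stand as DLT-free. Routine AE reporting to Day 56 is enough for the nominal 200 cGy course but not for 49 days of TMZ, and perhaps not for 34 fractions of 1.8 Gy or a delay of more than seven days.

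It would go too far to say that the 3+3 counts do not measure product toxicity. Attribution is written into part of the definition and may govern all of it. What the text supports is that the counts can be contaminated in either direction. Table 10 is arithmetically right, but it describes cohorts in which every patient is fully evaluable.

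The size is illustrative: the event and leaver rates are assumptions, and the structural points do not depend on them.

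**What to change.** Reconcile Sections 4.1, 4.2.1, 4.3, 10.2 and 10.3.1, and state the following once, in Section 4.2.1, with cross-references elsewhere.

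1. Only injected patients enter the DLT count, and the DLT period starts at injection (Day 0). State whether product attribution applies to every DLT item.
2. A patient is DLT-evaluable if injected and either had a DLT or completed the DLT period. Other injected patients are replaced for escalation decisions and kept in all safety tables.
3. Each escalation decision, and the six patients required at the MTD, use DLT-evaluable patients. The plan does not state that it would escalate on incomplete follow-up; this makes the requirement explicit.
4. AEs are collected through the later of Day 56 and the end of the DLT period.

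Section 4.6.2 and Table 3 give different fraction sizes. They should be reconciled because the end of the DLT period depends on them; this review takes no position on which applies.

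The cost is a wording amendment, occasional replacement of an early leaver (which may take accrual above 36), and a few extra days of AE collection in some patients.
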